1.3.1 Adverse events of specific interest

AEs of specific interest for safety monitoring include meningitis and potential Immune-Mediated Diseases pIMDs.

- Potential immune-mediated diseases (pIMD)

pIMDs are a subset of AEs that include autoimmune diseases and other inflammatory and/or neurologic disorders of interest which may or may not have an autoimmune aetiology. AEs that need to be recorded and reported as pIMDs include those listed below. However, the investigator will exercise his/her medical and scientific judgment in deciding whether other diseases have an autoimmune origin (i.e. pathophysiology involving systemic or organ-specific pathogenic autoantibodies) and should also be recorded as a pIMD.

When there is enough evidence to make any of the above diagnoses, the AE must be reported as a pIMD. Symptoms, signs or conditions which might (or might not) represent the above diagnoses, should be recorded and reported as AEs but not as pIMDs until the final or definitive diagnosis has been determined, and alternative diagnoses have been eliminated or shown to be less likely.

Events or outcomes not qualifying as adverse events or serious adverse events

1.3.2 Pregnancy

Female volunteers who are pregnant or intend to become pregnant will not be enrolled. Female subjects who become unexpectedly pregnant during of vaccination period (M0 to M2) will not receive additional doses of study vaccines but may continue other study procedures at the discretion of the investigator. While pregnancy itself is not considered an AE or SAE, any adverse pregnancy outcome or complication or elective termination of a pregnancy for medical reasons will be recorded and reported as an AE or a SAE.

The following should always be considered as SAE.

Spontaneous pregnancy loss, including:

- spontaneous abortion, (spontaneous pregnancy loss before/at 22 weeks of gestation)
- ectopic and molar pregnancy
- stillbirth (intrauterine death of foetus after 22 weeks of gestation).
- Any early neonatal death (i.e. death of a live born infant occurring within the first 7 days of life).
- Any congenital anomaly or birth defect identified in the offspring of a study subject (either during pregnancy, at birth or later) regardless of whether the foetus is delivered dead or alive.

Research Proposal Submission Form for a study involving human subject enrollment WITH specimen collection

Document No.: FTM ECF-033-01

Page 42 of 52

This includes anomalies identified by prenatal ultrasound, amniocentesis or examination of the products of conception after elective or spontaneous abortion.

Furthermore, any SAE occurring as a result of a post-study pregnancy AND considered by the investigator to be reasonably related to the investigational vaccines will be reported. While the investigator is not obligated to actively seek this information from former study participants, he/she may learn of a pregnancy through spontaneous reporting.

1.4 Detecting and recording adverse events and serious adverse events

1.4.1 Recording adverse events, serious adverse events and pregnancies

All AEs must be recorded into the appropriate section of the CRF, irrespective of intensity or whether or not they are considered vaccination-related.

1.4.2 Post-Study adverse events and serious adverse events

Investigators are not obliged to actively seek AEs or SAEs in former study participants. However, if the investigator learns of any SAE at any time after a subject has been discharged from the study, and he/she considers the event reasonably related to the investigational vaccines, the investigator will promptly notify the Study Contact for Reporting SAEs.

1.4.3 Active questioning to detect adverse events and serious adverse events

As a consistent method of collecting AEs, the subject should be asked a non-leading question such as: 'Have you felt different in any way since receiving the vaccines or since the previous visit?'

When an AE/SAE occurs, it is the responsibility of the investigator to review all documentation (e.g. hospital progress notes, laboratory and diagnostics reports) relative to the event. The investigator will attempt to establish a diagnosis pertaining to the event based on signs, symptoms, and/or other clinical information. In such cases, the diagnosis should be documented as the AE/SAE and not the individual signs/symptoms.

1.5 Assessment of Adverse Events and Serious Adverse Events

1.5.1 Assessment of intensity

The intensity of the following solicited AEs will be assessed as described:

Adverse Event	Parameter
Redness at injection site	Record greatest surface diameter in mm
Swelling at injection site	Record greatest surface diameter in mm
Bruising at injection site	Record greatest surface diameter in mm
Fever*	Record temperature in °C/°F
Other AEs	Record grading

**Research Proposal Submission Form
for a study involving human subject enrollment WITH
specimen collection**

Document No.: FTM ECF-033-01

Page 43 of 52

Severity grading criteria for the self-assessment for AEs.

GRADE 0	none
GRADE 1	noticeable, but no impact on activities
GRADE 2	noticeable and alters, but does not prevent daily activities
GRADE 3	prevents normal daily activities, and/or requires visits with a medical professional
GRADE 4	precipitates ER visit or hospitalization (these are, of course, also SAEs; Serious Adverse Effects).

*Fever is defined as temperature $\geq 37.5^{\circ}\text{C}$ / 99.5°F for oral, axillary or tympanic route, or $\geq 38.0^{\circ}\text{C}$ / 100.4°F for rectal route. The preferred route for recording temperature in this study will be axillary.

The investigator and designated study staff will assess non-solicited adverse events and will grade them according to Common Terminology Criteria for Adverse Events (CTCAE) Version 5.0.

In the rare case that an adverse event is not graded in the CTCAE, then that event should be graded as follows:

- Grade 1: Mild AE
- Grade 2: Moderate AE
- Grade 3: Severe AE
- Grade 4: Life-threatening or disabling AE
- Grade 5: Death related to AE

1.5.2 Assessment of causality

The investigator will assess the relationship between investigational vaccines and study antimalarial medications and the occurrence of each AE/SAE. The investigator will use clinical judgment to determine the relationship. Alternative plausible causes, such as natural history of the underlying diseases, concomitant therapy, other risk factors, and the temporal relationship of the event to the investigational vaccines and study antimalarial medications will be considered and investigated. The investigator will also consult the IB and/or Summary of Product Characteristics to determine his/her assessment. There may be situations when a SAE has occurred and the investigator has minimal information. However, it is very important that the investigator always makes an assessment of causality. The investigator may change his/her opinion of causality in light of follow-up information and update the SAE information accordingly. The causality assessment is one of the criteria used when determining regulatory reporting requirements. In case of concomitant administration of vaccine and study antimalarial medication, it may not be possible to determine the causal relationship of general AEs to the individual vaccine or medication administered. All solicited local (injection site) reactions will be considered causally related to vaccination. Causality of all other AEs should be assessed by the investigator using the following question:

Research Proposal Submission Form for a study involving human subject enrollment WITH specimen collection

Document No.: FTM ECF-033-01

Page 44 of 52

Is there a reasonable possibility that the AE may have been caused by the investigational vaccine or study antimalarial medications?

- YES : There is a reasonable possibility that the vaccines or study antimalarial medications contributed to the AE.
- NO : There is no reasonable possibility that the AE is causally related to the administration of the study vaccines or study antimalarial medications. There are other, more likely causes and administration of the study vaccines and study antimalarial medications is not suspected to have contributed to the AE.

If an event meets the criteria to be determined as 'serious', additional examinations/tests will be performed by the investigator in order to determine ALL possible contributing factors for each SAE.

Possible contributing factors include:

- Medical history.
- Other medication.
- Protocol required procedure.
- Other procedure not required by the protocol.
- Lack of efficacy of the vaccines, if applicable.
- Erroneous administration.
- Other cause (specify).

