DHA-PIP is the first line treatment for uncomplicated malaria in many malaria endemic countries in Asia and Africa and has an extraordinary robust safety profile (16-18). DHA-PIP is also very well tolerated. The main reported side effects are gastrointestinal upset (nausea, vomiting, abdominal pain and diarrhoea) as well as dizziness, headache and disturbed sleep. Rates of these side effects

Research Proposal Submission Form for a study involving human subject enrollment WITH specimen collection

Document No.: FTM ECF-033-01

Page 32 of 52

are generally < 10% and often <5% except for dizziness (~12%). There is no evidence that DHA-PIP can cause clinically significant QTc prolongation at therapeutic doses(19).

Primaquine (PQ)

Like all 8-aminoquinolones, primaquine is associated with haemolysis in G6PD deficient individuals in a dose-related relationship. To avoid any potential risk for haemolysis, participants will receive just a single low dose of primaquine (approximately 0.25mg/kg) on the day of vaccination, at each vaccine dose (for groups 1) and on Day 0 at each round of antimalarial drugs for three rounds (for group 3). This dose is safe even when administered to individuals with a genotype associated with severe G6PD deficiency(20). Other known side effects with primaquine administration include symptoms of gastritis and enteric complaints when administered for 14 days at large doses for the treatment of *Plasmodium vivax* malaria. Such abdominal complaints have not been observed when a single low dose primaquine is administered.

C2.2 Preventive and alleviative measures for risk

Phlebotomy

Participants' blood samples will be collected by well-trained medical personnel with aseptic technique to prevent infection or complications.

R21/Matrix-M™ vaccination

Volunteers will be vaccinated in a clinical area where Advanced Life Support trained physicians, equipment and drugs are immediately available for the management of any immediate post-vaccination serious adverse reactions. Participants will be observed closely for at least 30 minutes following administration of the vaccine. No SAEs attributable to the R21/Matrix-M™ were detected during the large trial in Burkina Faso.

Antimalarial medications

Dihydroartemisinin/piperaquine (DHA-PIP)

To exclude the possibility that pre-existing QTc prolongation results in AEs, the QTc of all volunteers will be measured and candidates with a QTc>450ms will not be enrolled.

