1.7 Holding rules and safety monitoring

No group holding rules will be pre-defined considering the evidence for a favourable safety profile of this candidate vaccine in Phase 2I infant evaluation.

Individual study participants who present with at least one of the following stopping rules will be withdrawn from further vaccine and/or drug administrations:

- Local reactions: upon investigator discretion.
- Systemic solicited adverse events: The subject develops a Grade 3 systemic solicited adverse event beginning within 2 days after vaccination/drug administration (day of vaccination and one subsequent day) and persisting at Grade 3 for >2 consecutive days.
- Unsolicited adverse events: The subject has any Grade 3 adverse event considered related to vaccination, persisting at Grade 3 for >2 consecutive days.
- The subject has a serious adverse event considered related to vaccination.
- The subject has an acute allergic reaction or anaphylactic shock following the administration of vaccine investigational product.
- Laboratory adverse events: The subject has any Grade 3 laboratory adverse event considered related to vaccination.

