5. STATISTICAL ANALYSES OF PRIMARY SAFETY ENDPOINTS

Safety analysis will be performed on patients allocated to receive vaccination. The percentage of subjects with at least one local AEs with at least one general AE (solicited and unsolicited) and with any AE during the 7-day or total follow-up period up to 28 days after the last vaccine dose and overall will be tabulated with exact 95% CI. The percentage of doses followed by at least one local AE (solicited and unsolicited), by at least one general AE (solicited and unsolicited) and by any AE during the 7-day or the total follow up period up to 28 days after the last vaccine will be tabulated with exact 95% CI. The same computations will be done for Grade 3 AEs, for any AEs considered related to vaccination and for any Grade 3 AEs considered related to vaccination. The percentage of subjects reporting each individual solicited local AE (any grade and Grade 3) and solicited general AE (any grade, Grade 3, any related, Grade 3 related, resulting in medically attended visit) during the 7-day follow-up period (Day 0-6) after each vaccine dose and overall will be tabulated for each group. Similarly, the percentage of doses followed by each individual solicited local and general AE will be tabulated, overall vaccination course, with exact 95% CI. For fever, the number and percentage of subjects reporting fever by half degree (°C) cumulative increments during the first seven days (Day 0-6) after each vaccine dose and overall will be tabulated. Similar tabulations will be performed for any fever with a causal relationship to vaccination and Grade 3 ($> 39.5^{\circ}\text{C}$) causally related fever. The percentage of subjects reporting unsolicited AEs from the date of the first vaccine dose up to 28 days after the last vaccine dose will be tabulated by group and by MedDRA preferred term with exact 95% CI. Similar tabulation will be done for Grade 3 unsolicited AEs, for any causally related unsolicited AEs and for Grade 3 causally related unsolicited AEs. The percentage of subjects reporting SAEs and pregnancies will be described in detail. The percentage of vaccinated subjects reporting AEs of specific interest (meningitis and pIMDs) will be described in detail.

Thus, in summary, the safety analysis will be as follows:

- Frequency (%) of occurrence of solicited local and general AEs within seven days (day of vaccination and six subsequent days) after each vaccination with exact 95% CI by group and severity.

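### One combined causality question cannot supply the tables of vaccine-related adverse events, and no derivation is stated

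*Protocol*

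**What the plan says.** Protocol Appendix B 1.5.2 sets the causality rule. Its opening says that the investigator assesses the relationship of both the vaccine and the antimalarials to each event, but the only question it supplies is combined: "Is there a reasonable possibility that the AE may have been caused by the investigational vaccine or study antimalarial medications". A yes is defined just as broadly: "There is a reasonable possibility that the vaccines or study antimalarial medications contributed to the AE". The section recognises the difficulty, saying that under co-administration "it may not be possible to determine the causal relationship of general AEs to the individual vaccine or medication administered". One class of event is settled by rule: "All solicited local (injection site) reactions will be considered causally related to vaccination".

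The outputs are worded for the vaccine alone. SAP section 5 repeats its AE computations "for any AEs considered related to vaccination and for any Grade 3 AEs considered related to vaccination". On fever it adds: "Similar tabulations will be performed for any fever with a causal relationship to vaccination". Its summary list includes SAEs related to the investigational vaccine. Protocol Appendix B 1.6 and 1.6.1 carry the same wording. Neither document plans a drug-related category or an either-agent category.

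The individual stopping rules in Protocol Appendix B 1.7 use the same attribution, for example "The subject has any Grade 3 adverse event considered related to vaccination".

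**The concern.** The analysis names a variable that the prescribed question does not yield, and the gap differs by arm. Arm 1 receives vaccine and drugs on the same day, Arm 2 vaccine only, and Arm 3 drugs only. One recorded answer therefore has three meanings.

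The primary objective is vaccine safety with and without antimalarials, so readers will look at Arm 1 against Arm 2. The symptoms overlap: nausea, vomiting, diarrhoea and headache are solicited systemic AEs (Protocol Table 8) and also listed side effects of DHA-PIP (Protocol C2.1). A drug-caused headache in Arm 1 that is marked yes would appear in a row titled as related to vaccination. Arm 2 has no counterpart to that event.

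**Working it through.** The documents state no figure on this point, so there is none to reproduce. The check is textual, followed by an illustration of size.

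**Step 1. Meaning of a yes, by arm** (general solicited AEs, unsolicited AEs and SAEs)

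| Arm | Products given | What a combined yes can mean | Does a vaccine-related label fit? |
|---|---|---|---|
| 1 (n = 50) | vaccine and drugs | vaccine, drug or both | not necessarily |
| 2 (n = 50) | vaccine | vaccine | yes |
| 3 (n = 20) | drugs | drug | no |

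**Step 2. What is outside the problem**

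- Solicited local reactions are assigned to the vaccine by rule.
- The safety endpoints in Protocol B6.3.1 and SAP 3.2 are occurrence of events. Relatedness plays no part in them.
- The safety summary table in the SAP (its Table 4) has no related row. The related tabulations appear only in the text of section 5.

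**Step 3. Illustration of size**

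Inputs:
- *d*, the proportion of Arm 1 participants with a drug-caused event marked yes. Protocol C2.1 gives only ceilings for most side effects: generally under 10%, often under 5%. Its one higher figure, about 12%, is for dizziness, which is not a solicited AE. I take *d* = 2%, 5% and 10% as assumptions.
- *v*, the proportion with a vaccine-caused general AE, assumed equal in Arms 1 and 2. The documents give no value. I take 5% and 30%.
- Drug-caused and vaccine-caused events are assumed independent, and every drug-caused event is assumed to be marked yes.

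Formula: Arm 1 row = 1 − (1 − *v*)(1 − *d*); Arm 2 row = *v*; excess = *d*(1 − *v*).

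| *v* (Arm 2 row) | *d* | Arm 1 row | Excess, points | Excess, participants of 50 |
|---|---|---|---|---|
| 30% | 2% | 1 − 0.70 × 0.98 = 31.4% | 1.4 | 0.7 |
| 30% | 5% | 1 − 0.70 × 0.95 = 33.5% | 3.5 | 1.75 |
| 30% | 10% | 1 − 0.70 × 0.90 = 37.0% | 7.0 | 3.5 |
| 5% | 2% | 1 − 0.95 × 0.98 = 6.9% | 1.9 | 0.95 |
| 5% | 5% | 1 − 0.95 × 0.95 = 9.75% | 4.75 | 2.4 |
| 5% | 10% | 1 − 0.95 × 0.90 = 14.5% | 9.5 | 4.75 |

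Under these assumptions the excess is positive whenever *d* is above zero. Only its size depends on the values chosen. If causality were recorded separately and attributed correctly, the excess in the vaccine-related row would be zero.

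**The case against.** The strongest reply is that little of what matters depends on relatedness. The endpoints are all-cause, and drug reactions in Arm 1 are real events of the combination. They would appear in the all-cause comparison of Arm 1 with Arm 2 however causality was asked. That stands: the combined question creates no events and only puts the wrong label on some of them. A reader might infer that it biases the primary safety endpoint. The documents do not support that.

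The CRF is listed in the submission package but is not among the documents, and it may hold separate fields. This also stands. It makes the mislabelling conditional on the combined answer feeding the tables. It does not supply the missing derivation.

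A reader might take 5% to 12% from Protocol C2.1 as the range of drug-related rates. That would turn a ceiling (often under 5%) into a floor and take the top from dizziness, which is not solicited. Nor is fever among the DHA-PIP side effects listed there, so the documents give no reason to expect a drug-caused shift in the fever rows, although their label rests on the same question.

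The planned output is descriptive, with exact intervals and no stated between-arm safety test. Even 15/50 against 19/50 gives 95% intervals of 17.9–44.6% and 24.7–52.8% (Fisher p = 0.53), so a shift of this size would not stand out. That is fair for any single row, but imprecision does not make a wrong label right.

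Finally, Arm 3 offers a randomised drug-only reference. This helps only in part. SAP 3.1 and section 5 define the safety analysis by receipt of, or allocation to, vaccine, although the safety table has a no-vaccine column. An all-cause reference also does not correct rows labelled as vaccine-related.

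**Conclusion.** The concern holds in a limited form. The protocol prescribes one causality answer for vaccine or antimalarials, the protocol and SAP analyses report vaccine-related events, and no rule connects them. Followed as written, the related rows for general, unsolicited and serious AEs carry a different meaning in each arm. In Arm 1 they can include drug reactions under a vaccine label, and in Arm 3 the label has no valid content.

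The size is not known from the documents. Under the assumptions above, the Arm 1 row is raised by 1.4 to 7.0 points at a vaccine-related rate of 30%, and by 1.9 to 9.5 points at 5%. These figures fall if some drug reactions are recognised and not counted as vaccine-related.

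The related tables, as planned, cannot support a statement about vaccine-caused events in Arm 1 against Arm 2. The all-cause tables can still support a statement about the combination.

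**What to change.** 1. In Appendix B 1.5.2 and on the CRF, replace the single item with two: related to vaccine, and related to antimalarials. Each takes yes, no or not separable.
2. In SAP section 5 and Appendix B 1.6 and 1.6.1, state that the vaccine-related rows come from the vaccine item, and show the not-separable events apart.
3. If the CRF is already fixed with only the combined item, retitle every such row as related to any study agent, and rest the Arm 1 against Arm 2 comparison on all-cause AEs.
4. If the CRF already holds separate fields, one sentence in each document saying so is enough.
5. Appendix B 1.5.2 and 1.7 must be reconciled, because the individual rules in 1.7 rest on relatedness to vaccination, which the combined item does not record. What those rules should be is for the sponsor and the investigator.

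The cost is one added CRF item and some table wording, or wording alone under step 3. The drawback is a not-separable category that could be large in Arm 1, where vaccine and drugs start on the same day. Reporting its size would at least show how far attribution was possible.

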1.5.3 Assessment of outcomes

The investigator will assess the outcome of all AEs (including SAEs) recorded during the study as:

- Recovered/resolved.
- Recovering/resolving.
- Not recovered/not resolved.
- Recovered with sequelae/resolved with sequelae.
- Fatal (SAEs only).

1.6 Safety (Analysis)

Safety and reactogenicity of the investigational vaccine will be analysed for the following

- Occurrence of solicited local and general AEs within seven days (day of vaccination and six subsequent days) after each vaccination.
- Occurrence of unsolicited AEs from the date of the first vaccination to 28 days after the last vaccination, according to the Medical Dictionary for Regulatory Activities (MedDRA) classification.
- Occurrence of SAEs (all, fatal, related to investigational vaccine) within 28 days (day of vaccination and 28 subsequent days) after each vaccination, according to the MedDRA classification.

Research Proposal Submission Form for a study involving human subject enrollment WITH specimen collection

Document No.: FTM ECF-033-01

Page 45 of 52

- Occurrence of SAEs (all, fatal, related to investigational vaccine) during the whole study period according to the MedDRA classification.
- Occurrence of AEs and SAEs leading to withdrawal from further vaccination from Dose 1 (Day 0) up to study conclusion (Day 180), according to the MedDRA classification, for each vaccinated subjects.
- Occurrence of pIMDs from Dose 1 (Day 0) up to study conclusion (Day 180), according to the MedDRA classification, for each vaccinated subjects.
- Occurrence of meningitis from Dose 1 (Day 0) up to study conclusion (Day 180), according to the MedDRA classification, for each vaccinated subjects.

